- ii) Participants will start with 1st and 2nd Line therapy as recommended by the AUA guidelines (AUA guidelines categorize treatments as 1st through 6th Lines of care) and we will record the numbers of participants that accelerate to higher lines of therapy. *Hypothesis: IC/BPS participants treated with mindfulness & yoga + Standard of care will have fewer participants who accelerate to higher Lines of care compared to those treated with Standard of care alone.*
- iii) Participants will record pain, function and other IC/BPS symptoms using validated questionnaires at baseline and at follow-up (approximately at 6 and 12 weeks of treatment). *Hypothesis: IC/BPS participants treated with mindfulness & yoga + Standard of care will have greater improvement in pain, function and other IC/BPS symptoms compared to participants treated with Standard of care alone, based on validated questionnaires.*
- iv) Cost-analysis will be performed comparing treatment groups. *Hypothesis: Cost analysis will find that those treated with mindfulness & yoga + Standard of care will incur less cost than Standard of care alone.*
- v) Qualitative outcomes will be obtained with an optional response during the weekly interviews to see how participant's feel their treatment is going. At a later time we may go back and enter quotes into qualitative software for analysis of themes. *Hypothesis: Patients in the mindfulness & yoga + Standard of care may feel more empowered about their health.*

2. Background

IC/PBS is a chronic urologic pain disorder associated with significant morbidity. It is defined by the American Urogynecological Association (AUA) as “a complex sensation (pain, pressure, or discomfort) perceived to be related to the urinary bladder, associated with lower urinary tract symptoms of more than 6 weeks duration, in the absence of infection or any other identifiable causeⁱ.” A 2015 survey of 1,982 patients with IC/BPS noted that, of the 180 treatment modalities, none were truly effective. In the survey, patients were surveyed about their usage of complementary and alternative medicine (CAM). Of those who responded, 84.2% had tried CAM and 55% had been recommended CAM by their physiciansⁱⁱ. There are many reasons as to why patients turn to CAM, including side effects experienced from traditional therapies, lack of efficacy and frustration with providersⁱⁱⁱ.

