We will perform an unmasked, randomized controlled trial comparing yoga and mindfulness impact on 1) treatment response 2) level of treatment required 3) pain, activity and quality of life for patients with IC/BPS compared to standard care alone as recommended by the AUA (Table 1). The target population will be those patients with IC/BPS who are cared for by the urogynecology, gynecology and urology specialties. After obtaining informed consent, women will be randomized to either yoga & meditation + Standard of care compared to Standard of care alone. Masking is not possible with this study design, as participants randomized to the yoga/mindfulness versus standard of care will clearly know their treatment arm.

4. Inclusion and Exclusion Criteria

4.1 We will recruit patients who present with IC/BPS per the AUA definition. To confirm the diagnosis of IC/PBS, We will also administer the O'Leary-Sant Interstitial cystitis Symptom Index and Problem Index to determine if patients are candidates for the study. We will also require that they have a physical exam performed in the past 2 years. As documented by others, a domain score of >6 will indicate applicability for enrollment in either symptom or problem domain^{xi}. Additional inclusion criterion include: evidence of an absent UTI (e.g. negative urine

PROTOCOL TITLE: MYPAICE: Mindfulness and Yoga for Pain with Interstitial Cystitis Evaluation

dipstick, a negative urinalysis or urine culture) within 2 months of enrollment as well as ability to speak and understand English or Spanish. We will recruit only patients who will be undergoing first-line and second-line treatment, as defined by AUA and who have not made treatment changes to their regimen in the past 4 weeks.

Patients will be excluded if they have:

- unevaluated hematuria,
- a history of recurrent urinary tract infection (UTI), as defined by AUA criteria as >2 culture-proven UTIs in 6 months or 3 UTIs in one year within the last 5 years,
- urinary retention, defined as a post-void residual (PVR) of >150 mL confirmed by bladder scan or catheterization,
- a history of augmentation cystoplasty or urinary diversion,
- a history of cyclosporine A use
- a history of pelvic radiation or chemotherapy in the past 2 years
- history of radiation induced cystitis
- if patients are currently pregnant or lactating or planning on becoming pregnant in the next 3-4 months

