7.1 The **primary endpoint** of our study is to determine the 3 month Global Response Assessment (GRA) in patients who perform yoga & mindfulness + Standard of care compared to patients who undergo Standard of Care alone, as well as a linear mixed model analysis of the GRA over time. Our **secondary endpoints** include: (i) proportion of patients in each group using accelerated lines of treatment (2-6) based on the AUA guidelines (i) the following validated questionnaires:), O'Leary-Sant Symptom and Problem Index (OSPI/OSCI), patient self-efficacy questionnaire (PSEQ-2), the PROMIS- Pain Interference Short Form 6b (PROMIS-PI and a visual analog scale, and the hospital anxiety and depression scale (HADS-A/D) (iii) Cost analysis potentially using, for example, the QALY scale if funds are found to support this.

7.2 We will not have any primary or secondary safety endpoints for which the study will be powered, as the interventions are extremely low risk (mindfulness and yoga).

7.3 Our **exploratory endpoints** are to investigate compliance to mindfulness and yoga treatment. Due to the extremely low-risk nature of therapeutic interventions, we do not have any safety endpoints.

8. Research Setting

8.1 The study will be performed at the University of New Mexico (UNM) Eubank Women's Primary Care Clinic and Sandoval Regional Medical Center (SRMC) Urogynecology clinics. These Urogynecology clinics are dedicated to care of women with pelvic floor disorders such as interstitial cystitis/bladder pain syndrome (IC/BPS), the target population for this study.

PROTOCOL TITLE: MYPAICE: Mindfulness and Yoga for Pain with Interstitial Cystitis Evaluation

8.2 Potential subjects will be recruited in the UNM Eubank and SRMC clinics when they present for care for IC/BPS, either in person or virtually via telephone or Zoom care visits. All patients will have a history and physical taken to determine their study eligibility, as well as a baseline BPIC-SS. Recruitment will take place either in private exam rooms at these clinics or over HIPAA-compliant telephone or Zoom conversation, and informed consent conversations regarding these clinics will take place via the same means.

8.3 There are no other laboratory tests in this trial other than would be routinely collected in the work up of IC/BPS.

8.4 There will not be involvement of any community advisory board.

8.5 There will not be any research conducted outside of the UNM HSC and its affiliates.

9. Resources Available

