approximately 10 minutes of meditation daily via a commercially available app (either Calm App or Headspace App, both of which are commercially readily available) and approximately 15 minutes of yoga via the online tutorial. Yoga & use of the meditation app is estimated to take approximately 30 minutes per day. Patients may engage in any other of the 1st Line AUA therapies as well taking over the counter medications (Table 1). Patients will be called weekly to ascertain treatment compliance and monitor their progress. If symptoms are not improving there will be the option to discuss other treatment options (e.g. accelerate to higher lines of therapy based on AUA guidelines) at 6 weeks.

Women assigned to the Standard of Care alone group will receive any 1st Line and 2nd Line treatments (excluding use of the online yoga and meditation app). Patients will also be called weekly to monitor progress and to ensure no treatment effect secondary to phone calls. If symptoms are not improving there will be the option to discuss other treatment options (e.g. accelerate to higher lines of therapy based on AUA guidelines) at 6 weeks. At the termination of the study women in the standard of care group will receive 3 months of Calm App.

At the 6 week follow-up phone call patients will be given the option for escalation of therapy. Patients will be given the opportunity to escalate their treatment for IC/PBS to higher lines of treatments: use of intravesical Botox or use of sacral neuromodulation. We will record any accelerated therapy used by the patient that may be added during study participation.

For participants who have completed the study but treatment escalation data was not properly captured in RedCap surveys, These participants will be notified via email through RedCap to complete this additional survey.

Outcome measures:

GRA: The Global Response Assessment is a validated tool to assess response to treatment. It is comprised of a single question and has been utilized widely in IC/BPS^{xiii}. This will be collected weekly. However, the primary outcome is the 12 week (3 month) result.

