THERAPY ESCALATION: We will record when and what women use that is greater than 1st line and 2nd line therapies during their participation in the study. They will discuss escalation of therapy with their provider and study personnel will record the additional therapy as an outcome measure. This will be utilized to perform cost utility analysis to determine if the intervention is cost-effective.

PSEQ-2: The Patient Self-Efficacy Questionnaire Short Form is a 2 question questionnaire that has been used in multiple chronic pain conditions to

PROTOCOL TITLE: MYPAICE: Mindfulness and Yoga for Pain with Interstitial Cystitis Evaluation

document feelings of self-efficacy. The Short form is validated in chronic pelvic pain^{xiv}. This will be collected at baseline and at 12 weeks.

PROMIS-PI: The PROMIS-Pain interference short form 6B is an NIH PROMIS measure that measures the extent that pain interferes with daily activities. It is comprised of 6 questions^{xv}. This measure will be collected weekly.

HADS: This is formally called Hospital Anxiety/Depression Scale. This is a 7 item inventory that assesses generalized anxiety including: tension, worry, fear, difficulty relaxing and restlessness^{xvi}. This measure will be collected at baseline and at 12 weeks.

Euroqol-5d. (EQ-5d) This is a validated measure utilized to measure health states^{xvii}.

O'Leary-Sant Interstitial Cystitis Symptom and Problem Index:

This validated survey assesses severity of symptoms and bother in IC/BPS and is commonly used for IC/BPS trials. Symptom index, which has been explicitly analyzed in a prospective trial to detect change, and problem index are to be separately analyzed^{xviii}

Data Analysis

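### The escalation endpoint in section 7.1 counts AUA lines 2 to 6, but 2nd-line therapy is part of the permitted start and section 12 records escalation only above it

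*Combined protocol and SAP*

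**What the plan says.** Section 7.1 lists as a secondary endpoint the "proportion of patients in each group using accelerated lines of treatment (2-6) based on the AUA guidelines".

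Other sections place the starting point differently:

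- Section 1.3(ii): "Participants will start with 1st and 2nd Line therapy as recommended by the AUA guidelines", after which "we will record the numbers of participants that accelerate to higher lines of therapy".
- Section 4.1: "We will recruit only patients who will be undergoing first-line and second-line treatment, as defined by AUA".
- Section 12, therapy escalation outcome: "We will record when and what women use that is greater than 1st line and 2nd line therapies". This outcome also feeds the cost-utility analysis.
- Section 12, 6-week option for both arms: the higher lines named are "use of intravesical Botox or use of sacral neuromodulation". Table 1 puts both botulinum toxin and neuromodulation in 4th line.
- Section 12, same paragraph: "We will record any accelerated therapy used by the patient that may be added during study participation", with no statement of the line from which a therapy counts as accelerated.

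Section 12 also plans a repeat survey. It is meant "For participants who have completed the study but treatment escalation data was not properly captured in RedCap surveys".

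The two arm descriptions in section 12 word background care differently. The yoga arm may use other 1st-line therapies and over-the-counter medications. The control arm receives any 1st- and 2nd-line treatment except the study's yoga video and app.

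**The concern.** A therapy that belongs to the permitted start cannot also mark escalation, yet section 7.1, which defines the endpoints, says that it does. Section 7.1 also leaves open whether any 2nd-line use counts or only a 2nd-line therapy newly started on study. The analysis text does not settle either question.

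Two consequences are possible, depending on what the REDCap forms hold. If 2nd-line use is captured, an analyst following section 7.1 would count it, and the endpoint would largely measure how common ordinary 2nd-line care is. If only therapy above 2nd line is captured, as the section 12 outcome text says, the analyst cannot follow section 7.1 and must choose another definition. In an unmasked trial that choice should not be made after the data are seen.

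Timing adds weight. Some escalation data are to be collected again by survey, and a survey built on the wrong threshold would carry the error into the recovered data.

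**Working it through.** **The plan's own figure.** The only sample size in the documents is for the GRA. For 26% versus 56% response (26% plus 30 points), two-sided alpha 0.05, pooled variance and no continuity correction, the two-proportion formula gives 41 per group with power 0.800. This matches section 5.3. It says nothing about the escalation endpoint, for which no rate or power is given.

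**Step 1: which lines each text supports.**

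| Place | Lines treated as escalation |
|---|---|
| 7.1 | 2 to 6 |
| 1.3(ii) | higher than the 1st- and 2nd-line start |
| 4.1 | none stated; entry is at 1st and 2nd line |
| 12, therapy escalation | above 2nd, so 3 to 6 |
| 12, 6-week option | examples are 4th line |
| 12, added therapy | no lower line stated |
| 18, potential benefits | none stated; describes women as choosing first-line treatment |

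Section 7.1 is the only place that numbers 2nd line among the accelerated lines. Section 18 leans towards it; sections 1.3(ii), 4.1 and the section 12 outcome text go explicitly the other way.

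**Step 2: effect of counting lines 2 to 6.** Let p be the true proportion reaching lines 3 to 6 in an arm, and s the share using 2nd-line therapy, equal in both arms and independent of escalation. The observed proportion is

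p + (1 - p) × s.

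Subtracting the arms gives

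observed difference = (1 - s) × (p_control - p_yoga).

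Equal use thus produces no false difference but shrinks a real one. At s = 100% both arms read 100% and the endpoint carries no information.

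**Step 3: illustration on assumed rates.** None of these rates is in the documents. Assume true escalation to lines 3 to 6 of 30% in control and 10% in yoga, with n = 41 per arm (borrowed from the GRA calculation) and two-sided 0.05. With p̄ the mean of the two proportions,

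power = Φ{ [ |p1 - p2| × √n - 1.96 × √(2p̄(1 - p̄)) ] / √(p1(1 - p1) + p2(1 - p2)) }.

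| s | Control | Yoga | Difference | Power |
|---|---|---|---|---|
| 0 (lines 3 to 6 counted) | 30% | 10% | 20 points | 62% |
| 20% | 44% | 28% | 16 points | 32% |
| 50% | 65% | 55% | 10 points | 15% |
| 80% | 86% | 82% | 4 points | 7% |

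For s = 20%, control is 0.30 + 0.70 × 0.20 = 0.44 and yoga is 0.10 + 0.90 × 0.20 = 0.28. Exact enumeration of the chi-square test gives 64.5%, 33.2%, 16.2% and 8.1% for the four rows, the same pattern. If only newly started 2nd-line therapy counts, s is the share of new starts and would be smaller.

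**The case against.** The best defence of lines 2 to 6 is that many women may enter on 1st-line care alone. Section 18 describes enrolled women as already choosing first-line treatment, and section 12 describes candidates as interested in self-care and behavioural modification. For such a woman, starting an oral agent or a bladder instillation is a step up. The word accelerated in section 7.1 also argues against counting a therapy she was already on. This reading is coherent and deserves a fair hearing. But it does not fit sections 1.3(ii) and 4.1, which put 2nd line in the start, or the section 12 outcome text, which leaves 2nd-line therapy out of what is recorded as escalation. That the protocol can be read both ways is itself a reason to state one definition.

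A second objection is that the dilution arises only if 2nd-line use is recorded, which the section 12 outcome text suggests it is not. This stands in part: dilution and mismatch with the data are alternatives and would not occur together. A reader might go further and infer that the section 7.1 count is impossible. The documents do not show that, because the REDCap forms are not included, treatment history is taken at baseline, and women are called weekly.

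A reader might also infer that counting 2nd-line use would create false-positive results. That would need unequal 2nd-line care caused by something other than the treatment, and the protocol mandates none. Randomisation is 1:1 after baseline data, so chance imbalance in baseline use is already within the test's nominal error. If yoga itself changed later 2nd-line starts, that would be a treatment effect on the broader endpoint.

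Nor do the arm paragraphs show that 2nd-line therapy is barred in the yoga arm. The sentence is permissive, the arm is titled as an addition to standard of care, sections 1.3(ii) and 4.1 apply to all women, and section 9.2 says the research requires no ordering of therapeutics. What remains is uneven wording.

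**Conclusion.** The definition in section 7.1 is wrong as written, because it conflicts with the starting therapy in sections 1.3(ii) and 4.1 and with the recording rule in section 12. It should be corrected. If applied, it would multiply the true difference by (1 - s), assuming 2nd-line use is equal across arms and independent of escalation. The actual loss cannot be determined, since the documents give no 2nd-line or escalation rate; the power figures show the direction and mechanism only. If 2nd-line use is not captured, the harm is instead an endpoint that does not correspond to its data.

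The reach is limited to one secondary endpoint, for which no power is claimed, and to the cost analysis that draws on it. Neither the GRA analysis nor its sample size is affected. The difference in background-care wording is a minor clarification.

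**What to change.** In section 7.1, replace the range 2-6 with 3-6 and define the endpoint as new use, after randomisation and up to week 12, of any 3rd- to 6th-line therapy in Table 1. Put the same definition in the section 12 escalation text and in the survey already planned for completers whose escalation data were not captured. Do this before that survey goes out and before the analysis.

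As a minor clarification, replace the two background-care sentences in section 12 with one for both arms: 1st- and 2nd-line therapies in Table 1 and over-the-counter medications are allowed, and the study's yoga video and meditation app are the randomised difference. For ongoing participants, record newly started 2nd-line therapy and tabulate it by arm as a description.

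The cost is one protocol amendment, a short staff memo and a REDCap item; no extra patients or visits are needed. There are two downsides. New 2nd-line starts no longer count as escalation and appear only descriptively, which the cost analysis should acknowledge. Any 2nd-line data collected retrospectively would be subject to recall error.

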The patients enrolled are already opting for first line treatment of their IC/PBS and potential use of over the counter medications. Participation in this study may help to improve an individual participant's condition, but it is also possible that the condition may not improve. There is no guarantee that any individual will personally benefit by participating in this research study. Women assigned to the yoga and meditation group will also receive 1) a video that will instruct them on use of yoga that may help with IC/BPS symptoms (designed by a physical therapist who specializes in caring for IC/BPS patients) and 2) a meditation app. that will be provided to the patient for approximately 3 months (the study will pay for it for that length of time). Participation in this study may provide information that may help other people who have a similar medical problem in the future. The literature supports improvement of QOL in similar conditions such as endometriosis or primary dysmenorrhea.

19. Recruitment Methods

The Urogynecology clinics at UNM Eubank, and SRMC have a large referral population of patients with pelvic floor conditions such as IC/BPS. Subjects will be identified in the clinics at UNM Eubank clinic and SRMC by investigators

PROTOCOL TITLE: MYPAICE: Mindfulness and Yoga for Pain with Interstitial Cystitis Evaluation

when they present either in person or virtually (telephone or Zoom visits) for visits for IC/BPS care. The patients will be counseled about possible treatment options for IC/BPS and they will be introduced to the study and provided with written information that may help them decide if participation in the study is right for them. Subjects are encouraged to consult with family, friends, and primary health care providers, as well as communicate any questions they may have before beginning the written consent process. We will request a waiver of HIPAA authorization for recruitment purposes.

If a woman declines to participate or is withdrawn from the study either by her desire or that of the research staff, she will be offered the same treatment options. Her follow up appointments will be the same regardless of participation in the study.

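### The escalation endpoint counts lines 2-6 in section 7.1 but only therapy above 2nd line in section 12, and some escalations may be missed at withdrawal

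*Combined protocol and SAP*

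**What the plan says.** Section 7.1 lists escalation first among the secondary endpoints, as the "proportion of patients in each group using accelerated lines of treatment (2-6) based on the AUA guidelines". The outcome-measures part of section 12, under therapy escalation, says instead: "We will record when and what women use that is greater than 1st line and 2nd line therapies".

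Starting or assigned care is described in several places:
- Section 1.3(ii): "Participants will start with 1st and 2nd Line therapy as recommended by the AUA guidelines". The outcome there is the number who go on to higher lines.
- Section 4.1: "We will recruit only patients who will be undergoing first-line and second-line treatment, as defined by AUA".
- Section 12, control arm: "Women assigned to the Standard of Care alone group will receive any 1st Line and 2nd Line treatments", apart from the study's yoga video and app.
- Section 12, yoga arm: other 1st-line therapies and over-the-counter medication are mentioned. 2nd line is not named, although this arm is given on top of standard care.
- Section 18: "The patients enrolled are already opting for first line treatment of their IC/PBS".

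At the six-week call, section 12 lets women "escalate their treatment for IC/PBS to higher lines of treatments: use of intravesical Botox or use of sacral neuromodulation". Table 1 places both in the fourth line. Section 12 adds: "We will record any accelerated therapy used by the patient that may be added during study participation".

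Section 14 allows, but does not require, staff to withdraw a woman who wants surgery. It provides for a GRA at withdrawal, for noting the reason if she offers it, and for use of her data up to that time. The catch-up escalation survey in section 12 is addressed to women who completed the study.

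**The concern.** The two sections disagree on whether line 2 is an event, and no text reconciles them. Escalation carries a directional hypothesis (fewer women in the yoga arm), and section 12 intends it for the cost-utility analysis, which section 7.1 makes dependent on funding. A threshold that reaches down into ordinary starting care measures something other than a move to more intensive treatment, and it weakens the contrast between arms. If the data are recorded as section 12 describes, the section 7.1 proportion may not be computable from the escalation variable at all.

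A second, smaller problem is capture. Table 1 places operative procedures in lines 3 and 6, so a woman who leaves in order to have surgery may be about to have the event that the endpoint counts. Nothing in section 14 turns that departure into an event or asks for her escalation status.

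**Working it through.** **1. The plan's own figure.** The only sample size is for GRA response (section 5.3): 26% against 56%, 80% power, alpha 0.05 (two-sided assumed).

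n = [1.960 × √(2 × 0.41 × 0.59) + 0.842 × √(0.26 × 0.74 + 0.56 × 0.44)]² / 0.30² = (1.363 + 0.558)² / 0.09 ≈ 41 per arm.

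This reproduces the stated 41. The documents give no rate, effect or power for escalation, so 41 per arm serves below only as the size for illustrations.

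**2. The two rules applied to the same women.**

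| Woman | Section 7.1 (lines 2-6) | Section 12 (above 2nd line) |
|---|---|---|
| Stays on 1st line | No | No |
| Continues the 2nd-line therapy she started on | Yes if read literally; no if accelerated means a move up after entry | No |
| On 1st line at entry, later adds a 2nd-line oral drug | Yes | No |
| Goes on to hydrodistension, Botox or neuromodulation | Yes | Yes |

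The third row differs on any reading.

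**3. What counting line 2 does to the comparison.** Let e be the proportion using lines 3-6 in an arm and s the proportion counted for 2nd-line use. Take s as equal in both arms and independent of e. Then:

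- rate under 2-6 = s + (1 - s) × e
- difference under 2-6 = (1 - s) × (e_control - e_yoga)

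All rates below are assumed. Power is for Fisher's exact test by full enumeration, 41 per arm, two-sided 0.05.

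| Lines 3-6, control vs yoga | s | Rates under 2-6 | Difference (points) | Power |
|---|---|---|---|---|
| 30% vs 10% | 0 (rule 3-6) | 30% vs 10% | 20 | 55% |
| | 20% | 44% vs 28% | 16 | 25% |
| | 50% | 65% vs 55% | 10 | 11% |
| | 75% | 82.5% vs 77.5% | 5 | about 5% |
| 20% vs 5% | 0 (rule 3-6) | 20% vs 5% | 15 | 43% |
| | 20% | 36% vs 24% | 12 | 16% |
| | 50% | 60% vs 52.5% | 7.5 | 8% |
| 40% vs 15% | 0 (rule 3-6) | 40% vs 15% | 25 | 66% |
| | 20% | 52% vs 32% | 20 | 39% |
| | 50% | 70% vs 57.5% | 12.5 | 16% |

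The direction is the same throughout. The size depends wholly on s and e.

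**4. Withdrawal.** With 41 per arm, each escalation left uncounted, with the woman kept as a non-event, moves her arm's proportion by 1/41 = 2.4 points. Suppose 12/41 against 4/41 truly escalate, a difference of 19.5 points. Missing three control escalators leaves 9/41 - 4/41 = 12.2 points. Missing three control and one yoga escalator leaves 9/41 - 3/41 = 14.6 points. The net effect depends on how losses fall between arms, which the documents do not show.

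**The case against.** The best defence is that the bracket in section 7.1 is a slip. The endpoint counts accelerated lines, not all use. Section 1.3(ii) starts women on 1st and 2nd line and counts those who go higher. Section 12 records therapy added during participation and sets the threshold above 2nd line, and its named examples are 4th line. On this view there is one bracket to correct, not two live rules. Most of this stands, and it shows which way to correct. It does not remove the conflict: section 7.1 is where the endpoint is defined, and a 2nd-line drug added after entry is still an event there and not in section 12.

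The defence also rules out two stronger inferences. A reader might conclude that every woman counts as escalated, giving 41/41 against 41/41. That requires unchanged starting care to be called accelerated and every woman to be on a 2nd-line therapy, and section 18 points to first-line treatment at entry. A reader might also fear that the rule could be picked after seeing the data. That risk is limited, because an escalation variable recorded as section 12 says would hold no 2nd-line events, and the documents do not say that other records would supply them.

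On withdrawal, the defence notes that it is discretionary, that escalation within the study is offered at six weeks and recorded, that women in both arms are called weekly, and that a volunteered reason is documented. This stands too. Some surgical departures will be identifiable, so it would be wrong to say that nothing but a GRA is obtained. What is missing is a required escalation status and a rule that makes such a departure count.

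**Conclusion.** The threshold in section 7.1 is wrong as written, and the rest of the plan shows that it should be above 2nd line. Counting line 2 would shrink a true difference in lines 3-6 to (1 - s) of its size, given equal and independent 2nd-line use in the arms. The documents supply neither s nor e, so the loss cannot be estimated, and the power figures are illustrations only.

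A reader might infer that 2-6 is biased towards yoga, because section 12 names 2nd-line treatment for controls and not in the yoga-arm paragraph. If 2nd-line use were, say, 60% against 30% with equal line 3-6 use e, the false difference would be (1 - e) × 30 points: 27 at e = 10% and 21 at e = 30%. The documents do not establish such an imbalance. Sections 1.3(ii) and 4.1 apply 1st- and 2nd-line care to all participants, and the yoga arm also receives standard care.

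The withdrawal gap is real but secondary: some escalations may go uncounted, in unknown number and direction. Both matters concern a secondary endpoint for which the trial was not sized. The primary GRA endpoint and its 41 per arm are untouched. The correction should be made, but it does not threaten the trial's main result.

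**What to change.** 1. In section 7.1, change the bracket from 2-6 to 3-6. Define the event, in both arms, as first use between randomization and week 12 of any therapy above 2nd line in Table 1, matching section 12. Tabulate new 2nd-line therapy by arm separately, and only if it is recorded.
2. In section 14, record escalation status at withdrawal together with the withdrawal GRA. Keep these women in the denominator, and add a sensitivity count in which withdrawals for surgical or higher-line treatment are treated as escalated.

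The cost is wording in two sections and one field on the withdrawal form, with no added participants or visits. The price is fewer events than under 2-6, so the result should be reported with a confidence interval. At an assumed 30% against 10% with 41 per arm, the half-width is 1.96 × √(0.30 × 0.70/41 + 0.10 × 0.90/41) = 0.168, about ±17 points.
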